### ***Aim of this study:***

Demonstrate that **intraoperative NOL-guided titration of fentanyl improves initial recovery characteristics**. All times below are relative to when sevoflurane anesthesia is discontinued.

**Primary hypothesis.** Pain scores (0-10 verbal response scale) at 10-minute intervals during the initial 60 minutes of recovery are less in patient with NOL-guided fentanyl than with routine care, with 1 point being considered a clinically meaningful difference

**Primary Outcome.** Pain Scores at 10-minute intervals during the initial 60 minutes of recovery

**Secondary hypothesis.** NOL patients are more likely to have a “good” pain scores, defined as < 5 (i.e., 0,1,2,3 or 4) across the measured intervals, with a relative 10% or more increase in the proportion of good scores being considered clinical meaningful.

**Secondary Outcome.** Whether or not the pain score at any measured interval is < 5.

We will also consider several exploratory hypotheses.

**Exploratory hypothesis 1.** Fewer analgesic rescue boluses are required in NOL-titrated patients during the initial 60 minutes of recovery.

**Exploratory hypothesis 2.** NOL-guided patients are no less alert (Ramsay score) during the initial 60 minutes of recovery than those given fentanyl per routine, based on a clinically meaningful non-inferiority delta of 20%.

**Exploratory hypothesis 3.** Emergence from anesthesia (discontinuation of sevoflurane anesthesia to extubation) is faster in NOL-guided patients.

**Exploratory hypothesis 4.** Fewer NOL-guided patients experience post-operative nausea and/or vomiting (PONV) **at least once** during the initial 60 minutes of recovery.

**Exploratory hypothesis 5.** There are fewer episodes of inadequate analgesia (too much or too little) in NOL-guided patients. Inadequate analgesia will be defined by systolic pressure  $\geq 140$  mmHg, heart rate exceeding 90 beats/min, diaphoresis, tearing, or movement. Excessive anesthesia will be defined by MAP  $< 65$  mmHg or BIS  $< 40$ . All values must return to normal for at least 15 minutes for a subsequent deviation to be

considered a new episode. The outcome for a patient will be the number of episodes.

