- 2) **NOL-guided opioid administration.** Clinicians will titrate fentanyl to keep NOL under 25 — *always using good clinical judgement for individual patients.*

NOL values exceeding 25 for more than 30 seconds will typically be treated with boluses of fentanyl 1 $\mu$ g/kg ABW, up to a maximum of 100  $\mu$ g per boluses, 5-minute intervals. Towards the end of the surgery (approximately 30-45 minutes before end of surgery, based on clinical judgment), the boluses of fentanyl will be reduced to 0.5  $\mu$ g/kg ABW, up to a maximum of 50  $\mu$ g per boluses, 5 minutes intervals. The target of a NOL score below 25 will be maintained until surgery ends.

Approximately 20-30 minutes before end of the surgery, a preemptive bolus of hydromorphone will be given intravenously per clinical routine;

- Patients younger than 70 years: 0.4 mg of hydromorphone for patients with an ABW <60 kg and 0.6 mg of hydromorphone for patients with an ABW > 60 kg
- Patients aged between 70 and 75 years: 0.4 mg of hydromorphone,
- Patients older than 75 years: 0.2 mg of hydromorphone.

Near the end of surgery, 4 mg ondansetron will be given intravenously per clinical routine. Upon completion of surgery, sevoflurane will be discontinued. Neuromuscular block will be reversed with sugammadex per clinician preference. At the end of the surgical procedure, patients will be extubated and transferred to the post anesthesia care unit (PACU).

Surgical pain will be treated with boluses of intravenous morphine/ hydromorphone per clinical routine by nurses blinded to intraoperative randomization. PCA will be activated upon arrival to PACU, per routine care. Generally, rescue boluses are given when verbal response pain scores are  $\geq 4/10$ , but consistent postoperative analgesic management will be at the discretion of the postoperative clinical team. Nausea and vomiting will be initially treated by intravenous injection of 4mg ondansetron per clinical routine. Alternative anti-emetics will be administered as clinically indicated.

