  - c. Muscle relaxants
  - d. Reversal agents
2. Events:
  - a. Induction
  - b. Intubation
  - c. Foley catheter placement
  - d. Incision
  - e. Insufflation
  - f. Trocar insertion
  - g. Discontinuation of sevoflurane
  - h. Extubation

In recovery, patients will be asked to rate their pain at rest on a 0-10 verbal response scale. Measurements will be taken at 10-minute intervals from awakening until 60 minutes has elapsed. Somnolent patients will be given a score of "S" for queries to which they are unable to respond. Patients will simultaneously be asked to rate nausea on a 0-10 scale. Sedation will be evaluated with the Ramsay score, also at 10-minute intervals.

Episodes of vomiting during the initial 60 minutes of recovery will be recorded. The time and dose of any administered postoperative analgesics or anti-emetics will be recorded.

The trial will end after 60 minutes of recovery and all subsequent management will be per clinical routine.

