**Exploratory outcome 1.** We will assess the treatment effect on the first exploratory outcome of number of analgesic rescue boluses using either a negative binomial regression (for count data), or else a proportional odds logistic regression if the negative binomial distribution is not a good fit to the data. In either case we will again adjust for the stratification variable.

**Exploratory Outcome 2.** We will assess the treatment effect on the Ramsey score measured at 10 minute intervals for during the first 60 minutes using a mixed effects proportional odds model to adjust for the within-patient correlation in the same manner as described for the sensitivity analysis for the primary outcome. We will test whether NOL is noninferior to routine care on the Ramsey score using a noninferiority delta of 1.2 for the proportional odds ratio, such that NOL will be deemed noninferior if the upper confidence limit for the odds ratio is less than 1.2. This will be accompanied by a 1-sided statistical test for noninferiority using the method described in Mascha and Sessler (2011), in which we use the parameter estimate and standard error of the treatment effect from the mixed effects model as well as the noninferiority delta in the test statistic, as

$$T_{NI} = \frac{\hat{\beta}_1 - \delta}{SE_{\hat{\beta}_1}}, \text{ where } \hat{\beta}_1 \text{ is the estimated log-odds ratio, } SE_{\hat{\beta}_1} \text{ is the estimated standard error, and } \delta \text{ is}$$

the log (delta), or log (1.2).

**Exploratory Outcome 3.** We will assess the treatment effect (in form of a hazard ratio) on the time to emergence from anesthesia using a Cox proportional hazards regression model adjusting for the stratification variable. We will check the proportional hazards assumption graphically and with the treatment-by-log (time) interaction. In presence of an interaction the treatment effect will be assessed using the log-rank test from a Kaplan-Meier analysis.

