## Human Subjects Protection

The experimental device PMD-200 from Medasense, Ramat-Gan) is CE marked and has been sold and used in the European Union for 3 years, and in Canada for 2 years. However, the NOL device has yet to be submitted for FDA clearance. The proposed pilot trial is designed to provide information that will help the investigators, Medasense, and the FDA optimally design a Phase 3 multi-center trial that might support FDA approval.

Typical pain scores during the initial phase of post-anesthetic recovery at the Cleveland Clinic Main Campus are 7/10, indicating poor pain control. The only aspect of our protocol that is non-standard is opioid titration to NOL. Pain scores could hardly be worse with NOL guidance, and in all cases, clinical judgement will prevail. Standard vital signs monitoring will continue to be used per current routine care. Our experienced anesthesia attending will never give patients clearly inadequate or excessive doses.

An important consideration is that opioid under-dosing and over-dosing is easily correctable. Most patients at the Cleveland Clinic and world-wide are under-dosed (as indicated by typically high initial pain scores) which is ameliorated simply by giving additional opioid. Over-dosing is also not especially serious since opioids can be antagonized by administration of small repeated doses naloxone until the right residual opioid effect remains. We thus request a non-significant risk device exemption for the proposed pilot trial.

Supplemental material includes sedation and delirium instruments, CE certificates, and safety and design documentation.

The following Adverse Events (AE) will be collected:

- All AEs with an anesthesia-related cause
- All adverse device effects (ADE)
- All Serious Adverse Events (SAE) (including sepsis events or related to opioid therapy)

Pre-planned interventions or occurrence of endpoints, including deviations in vital signs, specified in the CIP are not considered AEs, if not defined otherwise

Definitions according to ISO 14155:2011 will be used in this study.

Where the definition indicates “device”, it refers to the [PMD-100](#).

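### Rescue opioid and PCA act inside the 60-minute pain window, but the only rescue outcome counts boluses instead of measuring opioid dose

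*Combined protocol and SAP*

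**What the plan says.** **Window.** Under the study aim, "All times below are relative to when sevoflurane anesthesia is discontinued", and the primary outcome is "Pain Scores at 10-minute intervals during the initial 60 minutes of recovery". The Data Analysis section models 7 time points with fixed effects for treatment, time and chronic opioid use, and also assesses the treatment-by-time interaction. The secondary outcome (score below 5) uses the same scores.

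**Rescue.** In the Protocol section, blinded PACU nurses give intravenous morphine or hydromorphone. "Generally, rescue boluses are given when verbal response pain scores are" 4/10 or more, at the clinical team's discretion. In addition, "PCA will be activated upon arrival to PACU, per routine care".

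**Expected pain.** Human Subjects Protection says: "Typical pain scores during the initial phase of post-anesthetic recovery at the Cleveland Clinic Main Campus are 7/10".

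**Rescue outcome.** Exploratory hypothesis 1 reads "Fewer analgesic rescue boluses are required in NOL-titrated patients during the initial 60 minutes of recovery". The Data Analysis section takes the "number of analgesic rescue boluses using either a negative binomial regression", with proportional odds regression as the fallback.

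**Data held.** In Measurements, "The time and dose of any administered postoperative analgesics or anti-emetics will be recorded". No outcome is built on dose. The plan does not say whether a PCA delivery is a bolus, or how scores taken after rescue are to be interpreted.

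**The concern.** The trigger for rescue is the primary outcome variable itself, and rescue is given during the hour being scored. If titration leaves patients in the NOL arm more comfortable on waking, the routine arm will receive more opioid and its later scores will be pulled down. The treatment effect then shows up in two places: a pain difference smaller than the one before rescue, and a difference in opioid given. A reader needs both to judge the result, especially against the 1-point difference that the primary hypothesis calls clinically meaningful.

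The plan measures the second part poorly. A count gives a morphine bolus and a hydromorphone bolus the same weight, whatever their size, and bolus size is discretionary. If PCA deliveries are counted, the number depends partly on patient demand and device settings. If they are not, opioid given by PCA drops out of the outcome and may replace the nurse boluses that are counted. The treatment-by-time interaction can show the arms converging, but not whether rescue caused it.

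**Working it through.** **1. The plan's own figure.** Inputs from the sample size section: difference 1.25, SD 2.5, exchangeable correlation 0.60, 90% power, alpha 0.05 (taken as two-sided). With 7 scores the SD of a patient's mean is 2.5 × √[(1 + 6 × 0.60)/7] = 2.5 × √(4.6/7) = 2.027. Then n per arm = 2 × (1.960 + 1.282)² × 2.027²/1.25² = 55.3, rounded up to 56, so 112 in total. The t-based version gives 114; with 6 scores it gives exactly 116. The stated 116 is reproduced to within 3%. The maximum of 144 with the stated boundaries gives simulated power of about 0.90. No separate allowance for rescue appears in the calculation.

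**2. How common rescue would be.** Assume the 7/10 typical score is the control mean at the first reading, with SD 2.5 and scores rounded to whole numbers. The share scoring 4 or more is Φ[(7 − 3.5)/2.5] = Φ(1.40) = 92%. After a 1.25-point shift it is Φ[(5.75 − 3.5)/2.5] = Φ(0.90) = 82%.

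**3. What rescue could do to the contrast.** Simulation, 40,000 patients per arm: patient effect SD 2.5 × √0.6, residual SD 2.5 × √0.4, control mean 7, constant shift 1.25, scores rounded and bounded to 0–10, one rescue dose after each score of 4 or more. Each dose lowers all later scores by an **assumed** amount. Power at 58 per arm = Φ[(difference/SD) × √(58/2) − 1.96].

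| Points per dose (assumed) | Difference in 7-score mean | SD of patient mean | Ratio | Power, N = 116 |
|---|---|---|---|---|
| 0 | 1.13 | 1.87 | 0.60 | 0.90 |
| 0.5 | 1.01 | 1.66 | 0.61 | 0.91 |
| 1.0 | 0.82 | 1.36 | 0.60 | 0.90 |
| 1.5 | 0.66 | 1.13 | 0.58 | 0.88 |
| 2.0 | 0.56 | 0.97 | 0.58 | 0.87 |

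The first row is below 1.25, and its SD below 2.03, because scores are bounded. A repeat with 400,000 per arm moved no difference by more than 0.02 and put power between 0.86 and 0.91.

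At 1.0 point per dose the gap shrinks from about 1.14 at the first score to about 0.43 at the last. Patients receive 4.2 versus 3.4 rescue doses on average, not counting any dose after the final score. The difference missing from the pain scores reappears as opioid use.

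**4. Count against dose.** The simulation makes every dose equal, so there a count is as good as a dose. The trial does not: it has two drugs, discretionary sizes and PCA. That is where the count stops measuring opioid given, and where the recorded times and doses would supply the answer.

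**The case against.** **Pain under usual PACU care is a legitimate target.** It matters to patients and fits an aim about initial recovery. This stands. The remaining gap is that the plan does not declare this target or pair it with a sound measure of opioid given.

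**The size of the loss is not derivable.** The pilot and earlier data behind SD 2.5 and correlation 0.60 may already include rescue, and 1.25 may be meant as the difference with rescue allowed. The simulation applies these values before rescue, makes every rescue effect permanent and additive, and holds the untreated mean at 7 for the hour, whereas the plan gives 7/10 only for the initial phase. All of this stands; the table is an illustration.

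**A reader might infer that a real benefit will be missed.** Holding the SD of the mean at 2.027 and shrinking the difference to 1.00 or 0.75 lowers power at 116 patients to about 0.76 or 0.51. But score-triggered rescue acts most on the highest scores and compresses the spread too, so the ratio of difference to SD barely moves. The documents do not support a claim of serious power loss.

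**A reader might also infer that lower pain under NOL could be bought with more PACU opioid.** PACU nurses are blinded, and the Measurements section says all postoperative care and evaluation is blinded. Pain-driven rescue under blinding would mostly pull the arms together, so the documents give no mechanism for this reading.

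**Conclusion.** The concern holds as one of measurement and interpretation. Rescue and PCA lie inside the scored hour, rescue is triggered by the outcome, and the only rescue outcome is a count that does not measure opioid given. The pain difference in points may understate the difference before rescue. Under the assumed 0.5 to 2.0 points per dose it falls from about 1.13 to between 1.01 and 0.56, below the plan's 1-point threshold in three of the four settings, with power little changed.

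Those figures rest on assumed rescue effects and on planning values treated as pre-rescue; the documents settle neither. They do not show that the primary analysis is invalid or that the trial is underpowered on this account. The improvement is cheap and sharpens one exploratory outcome and the reading of the primary result. Priority: consider.

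**What to change.** 1. In Exploratory outcome 1, replace or supplement the bolus count with total opioid given from sevoflurane discontinuation to 60 minutes, nurse boluses plus PCA, in morphine equivalents. State the conversion used. Compare arms adjusting for the chronic-opioid stratum, on a log or rank scale if skewed. If the count is kept, say whether PCA deliveries are included.
2. State in the Data Analysis section that the primary analysis estimates pain under usual PACU rescue and is reported alongside the dose comparison.

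Two further steps are not recommended. Carrying forward the last score before the first opioid dose would come close to a first-score analysis, since 82% to 92% of simulated patients qualify for rescue at the first reading. Its power would be about 0.75, and it has no value to carry when opioid precedes any numeric score. Making attribution of a pain benefit depend on rescue dose not being higher would add a condition with no margin or test.

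**Cost.** SAP wording and one regression. Times and doses are already recorded, and the plan already uses morphine equivalents for baseline opioid use. The small downside is having to fix a conversion factor. Rescue practice is unchanged.

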## **Measurements**

Demographic and morphometric characteristics will be recorded, including sex, age, race, height, weight and opioid use in the last month (estimated morphine equivalents). Anesthesia clinicians cannot be blinded since they will need to titrate opioid administration to NOL. However, all postoperative care and evaluations will be fully blinded to randomization, thus preventing measurement bias. There will thus be separate teams of investigators for the intraoperative and postoperative portions of the trial.

All routine anesthetic monitoring will be used, and the results recorded electronically. Blood pressure will be evaluated continuously with an arterial catheter if clinically indicated; otherwise, blood pressure will be evaluated oscillometrically at 3-

minute intervals. Anesthetic drugs including end-tidal sevoflurane concentration, type and duration of surgery will also be recorded electronically at one-minute intervals. Inadequate analgesia will be defined by systolic pressure  $\geq 140$  mmHg, heart rate exceeding 90 beats/min, MAP  $< 65$  mmHg. Vasoactive drugs and episodes and duration of hypotension (mean arterial pressure  $< 65$  mmHg, occurrences of MAP  $< 60$  & MAP  $< 55$ ) will be recorded. Muscle-relaxant administration will be recorded as well.

During surgical stimulation under general anesthesia, a NOL of zero indicates no nociceptive response, and NOL of 100 indicates extreme nociceptive response. NOL values below 25 represent nociception/anti-nociception balance, suggesting either no nociception in the absence of noxious stimuli, or effective analgesia in the presence of noxious stimuli. NOL values are recorded by the Medasense monitor at 5-second intervals.

The clock on the NOL monitor will be synchronized to that driving the electronic record. Nociception will be continuously evaluated in all participating patients. However, values will be blinded to clinicians when patients are assigned to the routine opioid management group.

We will record the time of reversal agent administration wrist, the time at which sevoflurane is discontinued, along with the end of surgery (last stitch), eye opening, and extubation. Discontinuation of sevoflurane will be considered the end of anesthesia and the beginning of recovery.

The following will be recorded on the PMD-200 monitor, using the EVENTS button, as accurately as possible:

1. Medications administration:
  - a. Fentanyl
  - b. Vasoactive drugs
  - c. Muscle relaxants
  - d. Reversal agents
2. Events:
  - a. Induction
  - b. Intubation
  - c. Foley catheter placement
  - d. Incision
  - e. Insufflation
  - f. Trocar insertion
  - g. Discontinuation of sevoflurane
  - h. Extubation

In recovery, patients will be asked to rate their pain at rest on a 0-10 verbal response scale. Measurements will be taken at 10-minute intervals from awakening until 60 minutes has elapsed. Somnolent patients will be given a score of "S" for queries to which they are unable to respond. Patients will simultaneously be asked to rate nausea on a 0-10 scale. Sedation will be evaluated with the Ramsay score, also at 10-minute intervals.

Episodes of vomiting during the initial 60 minutes of recovery will be recorded. The time and dose of any administered postoperative analgesics or anti-emetics will be recorded.

The trial will end after 60 minutes of recovery and all subsequent management will be per clinical routine.

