## ***Data Analysis***

Randomized groups will be assessed for balance on baseline characteristics using the standardized differences, defined as the difference in means or proportions divided by the pooled standard deviation. An absolute standardized differences  $> 0.10$  will be considered as imbalanced. We will use modified intent-to-treat such that all randomized patients receiving any of the study intervention (either one, even if the incorrect treatment was applied) will be included in the primary analyses.

**Primary outcome.** We will assess the treatment effect of NOL guided analgesic management versus routine care on mean pain score with the first 60 minutes of the recovery period using a linear mixed effects model adjusting for within-patient correlation across the 7 time points, and fixed effects for intervention, time (as categorical) and the stratification variable of pre-operative chronic opioid use. We will also assess the treatment-by-time interaction. We will decide on the most appropriate correlation structure empirically, using the AIC criterion, and considering either AR(1), exchangeable, or other correlation.

**Sensitivity analysis.** As a sensitivity analysis we will assess the treatment effect on pain score using a mixed effects proportional odds model in which we consider patient as a random effect while estimating the proportional odds ratio for patients having a better outcome on NOL than standard care, again adjusting for the stratification variable.

**Secondary outcome.** We will assess the treatment effect of NOL versus routine care on the proportion of patients with pain score less than 5 (i.e., 0-4) across the 7 time points using a generalized linear mixed effects model with a binary outcome ( $<5$  or  $\geq 5$ ), log link

(to be able to estimate relative risk), patient as random effect and modeling the within-subject serial correlation using an R matrix (considering autoregressive AR(1), exchangeable and unstructured correlation structures), with treatment group and the stratification variable as fixed effects. We will also assess the treatment-by-time interaction. Results will be reported as the relative risk (95% CI) of having a “good” pain score over time in NOL versus routine care.

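### Pain queries scored S have no place in any pain model, and the secondary model lists no time effect, so its relative risk rests on an unstated coding of S

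*Combined protocol and SAP*

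**What the plan says.** In the Measurements section of the combined protocol and SAP, pain at rest is asked for every 10 minutes on a 0-10 scale, and "Somnolent patients will be given a score of 'S' for queries to which they are unable to respond". Sedation is scored on the Ramsay scale on the same schedule.

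The Data Analysis section then specifies three analyses of pain:

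- **Primary:** a "linear mixed effects model adjusting for within-patient correlation across the 7 time points", with fixed effects for intervention, categorical time and the chronic-opioid stratum.
- **Sensitivity:** "As a sensitivity analysis we will assess the treatment effect on pain score using a mixed effects proportional odds model".
- **Secondary:** the proportion of scores below 5 "across the 7 time points using a generalized linear mixed effects model with a binary outcome", with a log link. Its listed fixed effects are treatment and stratum only. A treatment-by-time interaction is to be assessed as well.

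The Aim section defines the secondary outcome as "Whether or not the pain score at any measured interval is < 5" and sets the meaningful effect as an improvement "with a relative 10% or more increase in the proportion of good scores being considered clinical meaningful", that is, a relative risk of 1.10.

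Nowhere does the plan say whether S is missing, imputed, ranked, good or not good. It has no missing-data rule and no plan to tabulate S by arm. The modified intent-to-treat definition decides which patients are included, not which readings.

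**The concern.** A letter cannot enter a linear model, an ordinal model without an assigned rank, or a binary split at 5. Followed literally, the plan omits every S reading. That is valid only if, given what the model contains, failure to answer is unrelated to the pain score that would have been given. The intervention changes opioid dosing, which can plausibly change somnolence, so the assumption needs testing.

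The secondary model has a further weakness. If S is commonest early, when pain is likely to be highest, an arm that loses more early readings keeps a larger share of later, lower-pain readings. Without a time effect, that change in mix is read as a treatment effect.

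At stake is the meaning of the secondary relative risk. If the coding of S is left until data are seen, the same records could support different conclusions.

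**Working it through.** **Inputs from the plan** (Sample size justification): SD 2.5, exchangeable correlation 0.60, design difference 1.25, 90% power, significance level 0.05 (two-sided assumed). As a check, the SD of the mean of six readings is 2.5 × √((1 + 5 × 0.60)/6) = 2.041, and a t-based two-sample calculation gives the stated total of 116. Seven readings give 114. Sample size is not at issue here.

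**Assumptions.** The plan gives no S rates and no good-score rates. All those below are illustrative.

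**1. Missing time effect, secondary outcome.** Assume no true pain difference, mean pain falling linearly from 6.5 to 4.5 over seven readings, and S at random in the first three readings at 10% (routine) and 40% (NOL). Take the probability of a good score as Φ((4.5 − mean)/2.5), where 4.5 is the continuity-corrected cut for scores of 4 or less. These probabilities sum to 0.761 over the first three readings and 1.686 over the last four.

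- Routine, good scores per patient among answered queries: 0.9 × 0.761 + 1.686 = 2.371, over 6.7 answered readings = 0.354.
- NOL: 0.6 × 0.761 + 1.686 = 2.143, over 5.8 = 0.370 (0.3695 before rounding).
- Relative risk with S omitted: 0.3695/0.3540 = **1.04**. Compared within time points it is 1.00, because each reading has the same good-score probability in both arms.
- S counted as not good: 2.143/2.371 = 0.90.
- S counted as good: (2.143 + 1.2)/(2.371 + 0.3) = 1.25.

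If S is also related to pain (latent correlation from −0.6 to 0.6), simulation puts the S-omitted relative risk at about 0.98 to 1.12. It is highest when S falls on high-pain readings and lowest when S goes with low pain. S as not good gives about 0.85 to 0.97, and S as good about 1.2 to 1.3. With S rates of 5% and 10%, the S-omitted value stays within 0.98 to 1.02.

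These are ratios of pooled proportions, not fits of the planned log-link mixed model, so they show direction and order of size.

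**2. Coding of S, secondary outcome.** Let s be the share of queries scored S and g the share of good scores among answered queries, with N for NOL and R for routine.

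- S omitted: RR = gN/gR
- S not good: RR = (gN/gR) × (1 − sN)/(1 − sR)
- S good: RR = [gN(1 − sN) + sN]/[gR(1 − sR) + sR]

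| gN, gR | sN, sR | S omitted | S not good | S good |
|---|---|---|---|---|
| 60%, 50% | 25%, 5% | 1.20 | 1.20 × 0.75/0.95 = 0.947 | 0.70/0.525 = 1.333 |
| 60%, 50% | 5%, 5% | 1.20 | 1.20 | 0.62/0.525 = 1.18 |
| 44%, 40% | 5%, 15% | 1.10 | 1.10 × 0.95/0.85 = 1.229 | 0.468/0.49 = 0.955 |

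At the plan's meaningful value of 1.10 and 5% S on routine care, coding S as not good takes the relative risk below 1 once NOL S exceeds 1 − 0.95/1.10 = 13.6%.

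**3. Primary outcome.** A simulation (40 replicates per scenario, 72 patients per arm, overall S 25% NOL and 5% routine, true difference 1.25) fitted the mixed model with S omitted and compared it with the complete-data difference:

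- S unrelated to pain: −1.27 against −1.27.
- S on low-pain readings: −1.08 against −1.26.
- S on high-pain readings: −1.50 against −1.32.

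The shift is about 0.2 points either way with no change of sign. The scenario in step 1 gave at most about 0.12 points.

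**The case against.** A reader might infer that over-sedated patients silently leave the comparison and that the more sedated arm is credited with better pain control. The documents do not support that reading.

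- Single queries drop out, not patients. In the simulations almost no patient had all seven readings scored S. S is recorded deliberately, and sedation is tested by the Ramsay noninferiority analysis, though only as an exploratory outcome.
- Credit to the sedated arm requires S to be unrelated to pain or to fall on high-pain readings. If S goes with low pain, omitting it is close to neutral or slightly unfavourable to that arm.
- The plan does not show which arm will have more S. The Specific Aims and exploratory hypothesis 3 expect NOL patients to wake sooner.
- The change of direction comes mainly from recoding S under assumed unequal rates. Counting S as not good is a different endpoint: with no pain difference it gave 0.90 in step 1, an apparent harm that reflects sedation alone.
- The treatment-by-time fit must itself contain time, so time is not wholly absent from the secondary analysis.
- Early clustering of S depends on the clock. The Aim section says "All times below are relative to when sevoflurane anesthesia is discontinued", whereas Measurements starts the readings at awakening, which would leave fewer S scores.

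All of this stands, and it limits the size of the problem. It does not supply a rule for S, nor a time effect in the model that yields the reported relative risk.

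**Conclusion.** The point holds as a gap in the analysis specification. S readings drop out of all three pain models under an assumption that the plan neither states nor tests.

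For the secondary outcome, omitting time allows a spurious relative risk of about 1.04 under a large assumed imbalance in early S (10% versus 40%), and no more than about 2% either way at 5% versus 10%. How S is coded matters far more when rates differ: 0.95 to 1.33 around an S-omitted 1.20 in the worked example. With equal rates it hardly matters. For the primary outcome the effect is modest, about 0.1 to 0.2 points against a design difference of 1.25, with no reversal in the scenarios tried.

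Every size rests on S rates that the documents do not give. No particular direction of bias is established. The point deserves correction because the remedy is nearly free, not because the primary result is in doubt.

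**What to change.** Before unblinding, amend the analysis section as follows.

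1. Add time as a categorical fixed effect to the secondary model, as the primary model already has. This removes the part due to unequal early loss, but not bias from S depending on pain at a given time point. The bounds in item 3 address that.
2. Report the number of S scores by arm and time point.
3. State that S is omitted in the main analyses, and prespecify bounding sensitivity analyses. For the secondary outcome, count S as not good and then as good. For the primary, run the planned proportional-odds model with S ranked worst and then ranked as lowest pain. Interpret both alongside the Ramsay results.

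The bounds should inform interpretation and should not become a new success rule. Requiring agreement in both directions would change the operating characteristics of a group sequential trial planned for 90% power. Making S as not good the main secondary definition would change the endpoint.

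The cost is a few extra model runs on data already collected, and possibly a less clear-cut secondary result.
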